### 6.2. Investigational device(s) and comparator(s)

Refer to section 2 for the description of devices that may be used in this investigation.

### 6.3. Subjects

Potential subjects may be recruited and enrolled according to the criteria below. [REDACTED]

[REDACTED]

[REDACTED]

[REDACTED]

#### 6.3.1. Inclusion Criteria (Eligible Subjects)

- Subject is a full-term newborn (37 weeks) – up to 18 months of age.
- The parent(s) or guardian(s) of minor subjects are able to read and communicate in English and understand the study and the risks involved.

#### 6.3.2. Exclusion Criteria (Ineligible Subjects) (\* = Per study staff discretion)

- Subject has underdeveloped skin.
- Subject has a skin condition and/or deformity at the planned application site, which would preclude sensor placement and measurements.
- Subject has an absence or deformities of limbs or severe edema, which would interfere with sensor application or prevent the proper fit of the sensors.
- Subject has any medical condition which in the judgment of the investigator and/or study staff, renders them ineligible for participation in this study or subject is deemed ineligible by the discretion of the investigator/study staff.

#### 6.3.3. Expected Duration of Each Subject's Participation

The expected duration of each subject's participation in the lab will be approximately 120 minutes.

Subjects may also participate in home studies that may last up to 2 days (48 hours).

#### 6.3.4. Withdrawal of Subjects

Subjects must be withdrawn under the following circumstances:

- The subject's parent withdraws permission.
- Discretion of investigator/study staff.
- Subject safety concerns.

#### 6.3.5. Re-contacting Subjects

If the subject's parent(s) or legal guardian fail to provide proper documentation on their individual permission form for any study, Masimo has the right to re-contact the subject's parent(s) or legal guardian and ask them to return to the clinical lab in order to properly complete the permission form or subject bill of rights. The subject will be compensated for travel.

The subject's parent(s) or legal guardian will also fill out other study documents. These documents aid in the collection of data, tracking subject count, etc. If the subject's parent(s) or legal guardian fails to provide proper documentation on other documents, the subject will not need to return to the laboratory.

in order to complete those specific forms. However, Masimo has the right to re-contact the subject's parent(s) or legal guardian and ask them to return to the clinical lab in order to properly complete these documents if seen as necessary by study staff.

The subject's parent(s) or legal guardian will be re-contacted via phone or email and be asked to return as soon as possible.

## 6.4. Procedures

### 6.4.1. Recruitment and Pre-Screening

#### 6.4.1.1. Advertisement and Recruitment

Recruitment materials are posted publicly in local newspapers, advertisement websites (e.g., craigslist), schools/universities, social media platforms (e.g., Facebook), bulletins, flyers, handouts, child daycare centers, etc. We will recruit human subjects, which will include members of the general public .

#### 6.4.1.2. Phone Screening

Once the potential subject's parent(s) or legal guardian see the recruitment material (e.g., advertisement), they can contact us to inquire more details about the study. The recruitment process is managed by the designated person(s) who is trained for phone screening/scheduling.

Virtual or In-person appointments are made once the phone screening process is completed and the person screening the subject determines if they qualify for the study based on inclusion/exclusion criteria.

Information from the screening will be kept in a database located within the firewall-protected Masimo internal network with user level access control enforced domain log in. Additionally, the database is encrypted and password protected. The information is kept to contact the subject's parent(s) for other studies they may qualify for or for instance, to track subjects who call in and provide false information only to qualify.

#### 6.4.2. In-Person Permission and Screening

The subject's parent(s) or legal guardian may be asked to provide a copy of their valid government photo ID and/or Social Security Number (SSN) card to complete a W-9 form. A W-9 form might need to be completed to report earnings to the Internal Revenue Service (IRS).

Foreign persons (a foreign person includes a nonresident alien individual and certain foreign entities that are not U.S. persons) may be asked to provide a copy of U.S. immigration documents/Tax ID Number (TIN) or equivalent, and to complete a W-8BEN form to report earnings to the Internal Revenue Service (IRS).

Copies of these forms of identification may be stored electronically. The confidentiality and retention of these documents will be protected to the extent provided and required by the law.

Copies of the SSN and ID card are kept to verify subjects' identities or for instance, to track subjects who provide false identification.

For all subjects, a parent or legal guardian must be present throughout the duration of the study. The parent or legal guardian must read and sign the parental permission form for their child to participate, using our informed consent process.

The paper parental permission form must be stamped with a current IRB approval. Due to the limitations of the electronic parental permission form, the form may not be stamped with a current IRB approval; however, the IRB will review and approve the electronic document prior to implementation. The electronic parental permission form will contain indicators that show the version of the form. No study-related activities will be conducted until the parental permission form is completed by the subject's parent(s) or legal guardian.

Study documents such as the Confidentiality Agreement and Volunteer Payment Form will be

completed by the subject's parent(s) or legal guardian.

A parent or legal guardian must complete the health assessment on the subject's behalf. Subjects who do not meet the inclusion criteria and/or meet exclusion criteria will not be eligible to participate in the study.

Subject demographic information such as age, sex, skin tone, ethnicity, height, and weight will be collected. These may be recorded for data analysis and/or subject safety monitoring purposes.

During the study, subjects may be recorded using photography and/or videography. The recordings may include sound. These recordings may capture identifying features. These recordings may be used in research, product development, product testing, training, and comparison study purposes. In studies with photography and/or videography, the subject's parent(s) or legal guardian will give permission for the recordings and/or observational group prior to the start of any study-related activities.

### 6.4.3. Virtual Permission and Screening

The parent or legal guardian must read and sign the parental permission form for their child to participate, using our informed consent process.

The parental permission form may be sent out electronically or on paper. The paper parental permission form must be stamped with a current IRB approval. Due to the limitations of the electronic parental permission form, the form may not be stamped with a current IRB approval; however, the IRB will review and approve the electronic document prior to implementation. The electronic parental permission form will contain indicators that show the version of the form. No study-related activities will be conducted until the parental permission form is completed by the subject's parent(s) or legal guardian.

Study documents such as the Confidentiality Agreement and Volunteer Payment Form will be completed by the subject's parent(s) or legal guardian.

Delegated lab personnel will call the parent or legal guardian to complete the health assessment on the subject's behalf. Subjects who do not meet the inclusion criteria and/or meet exclusion criteria will not be eligible to participate in the study.

Subject demographic information such as age, sex, skin tone, ethnicity, height, and weight will be collected over the phone. These may be recorded for data analysis and/or subject safety monitoring purposes.

The subject's parent or legal guardian may be asked to provide photos or videos of sensor placement on the subject. In studies with photography and/or videography, the subject's parent(s) or legal guardian will give permission for the recordings and/or observational group prior to the start of any study-related activities.

### 6.4.4. In-Person Sensor Placement Procedure and Data Collection

Prior to the placement of INVSENSOR00061, the subject may be observed for crying, restlessness, etc. If applicable, the observations will be recorded on the subject's CRF.

The area of sensor application may be prepped using an alcohol pad or comparable. INVSENSOR00061 will be placed on the opposite foot of the FDA-cleared sensor.

An FDA-cleared sensor will be placed on the subject's foot, depending on subject's weight, following manufacturer's DFU and the study's procedure manual. Continuous data from the pulse oximeter will be collected.

INVSENSOR00061 will be paired via Bluetooth connection to data collection software on a laptop or a phone. Upon successful Bluetooth pairing of the investigational device, data collection will be initiated on the data collection software and data will be obtained continuously (SpO2, PR, [REDACTED]).

Data will be collected for approximately 90 minutes using the data collection software. The subject may be observed for crying, restlessness, etc. If applicable, the observations will be recorded on the subject's CRF.

Standard of care and the study sensor placement locations, study sensor ID/lot number, the subject's reaction prior to and after sensors placement, observations during data collection, and other relevant information will be recorded in the CRF.

### 6.4.5. Virtual Sensor Placement Procedure and Data Collection

The subject's parent(s) or legal guardian may be asked to prep the area of sensor application using an alcohol pad or comparable which will be provided. INVSENSOR00061 may be placed on the opposite foot of the FDA-cleared sensor.

An FDA-cleared sensor may be placed on the subject's foot, depending on subject's weight, following manufacturer's DFU. Continuous data from the pulse oximeter will be collected via Bluetooth.

INVSENSOR00061 will be paired via Bluetooth connection to data collection software on a laptop or a phone. Upon successful Bluetooth pairing of the investigational device, data collection will be initiated on the data collection software and data will be obtained continuously (SpO2, PR, [REDACTED]).

Data may be collected overnight while the subject is asleep for up to two days using the data collection software. The subject may be observed for crying, restlessness, etc. If applicable, the observations will be recorded in the data collection device.

Standard of care and the study sensor placement locations, study sensor ID/lot number, the subject's reaction prior to and after sensors placement, observations during data collection, and other relevant information may be recorded in data collection device.

### 6.4.6. Ending Procedure

At the conclusion of the procedure, the sensor(s)/device(s) will be removed and returned to Masimo either by mail or in-person drop-off if applicable.

The subject's parent(s) or legal guardian will be paid according to the compensation breakdown on the permission form.

### 6.5. Monitoring plan

A separate document for the study monitoring plan will be developed and followed to ensure subject safety and GCP compliance.

### 7. STATISTICAL DESIGN AND ANALYSIS

This is a single center prospective study that will use a convenience sampling of 25 subjects. A minimum of 25 subjects are being targeted for this study because it exceeds the 15 typically recommended by the FDA to evaluate the human factors and usability of a device and the number is aligned to the number of subjects calculated by Masimo in which the statistical value of additional subjects diminishes in the Arms error distribution analysis.

As part of the additional data analysis for this study, the [REDACTED] accuracy values may be calculated against the respective reference. The purpose of this study is to assess the form, fit, and function, the analysis is not intended for specification validation. The performance specification validation is outside the scope of this convenience sample study.

- Accuracy (root mean square error [ARMS])

$$A_{RMS} = \sqrt{\frac{\sum_{i=1}^n (Test - Ref)^2}{n}}$$

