## 3. JUSTIFICATION FOR THE DESIGN OF THE CLINICAL INVESTIGATION

Pulse oximetry is commonly used as a standard of care (SOC) in critically ill patients in intensive care units and used in surgical operations to monitor oxygen saturation (SaO2) levels. The advantage of this noninvasive technology is that it allows for the detection of hypoxia [1].

Oxygen saturation levels represent the ratio between oxyhemoglobin (oxygenated) and deoxyhemoglobin (non-oxygenated) present in the blood [2]. The pulse oximeter works by measuring frequencies of light, which correspond to the type of hemoglobin present in the blood. By isolating the pulsatile signal, the oxygen saturation of arterial hemoglobin can be estimated.

Masimo Corporation develops noninvasive medical technologies such as Masimo Signal Extraction Technology (SET®), which is incorporated in Masimo SET® pulse oximeters and adhesive sensors. Masimo SET® signal processing is designed to overcome limitations of conventional pulse oximetry technologies distinguishing between pulsating blood in arterial and venous blood at the measurement site. Masimo SET® pulse oximeters have been FDA-cleared for the monitoring of SpO2, PR, and RRp in motion and non-motion conditions. Studies have found fewer false alarms and more accurate true alarm detection. Masimo SET® pulse oximeters use advanced signal processing algorithms to filter out noise, such as moving venous signals, to help improve the detection of the true arterial oxygen saturation [3].

The objective of this study is to evaluate the form, fit, and function of INVSENSOR00061 when used on newborn and infant subjects. To evaluate the form, fit, and function, the study will look to collect data on the application, fit, and ability to obtain the supported parameters on the intended study population. To confirm the acceptability of the form, fit, and function for each subject a standard of care FDA cleared adhesive sensor will be applied to each subject as a reference. The standard of care sensor is provided as reference in the study because it is possible that a very small population of subjects may have physiologies that may make the supported parameters difficult to obtain.

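### Does the optional A_RMS formula in Section 7 need a defined index, a subject level and a lab/home rule?

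*Combined protocol and SAP*

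**What the plan says.** Section 7 describes accuracy as an additional analysis: "accuracy values may be calculated against the respective reference". It gives one formula, the square root of the sum of (Test - Ref)^2 over i = 1 to n, divided by n. It does not say whether i is a time-matched reading, a recording or an infant, and it gives no weighting rule or lab/home rule. No other section supplies one. The redaction in that sentence sits where the parameter names would be, so it does not account for the gap. Section 7 also limits the purpose: "the analysis is not intended for specification validation".

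The two settings differ in recording length. Section 6.4.4 (lab) says "Data will be collected for approximately 90 minutes using the data collection software". Section 6.4.5 (home) says "Data may be collected overnight while the subject is asleep for up to two days using the data collection software". Section 6.3.3 makes home studies an optional addition with a ceiling of 48 hours.

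The settings also differ in how firmly a reference sensor is required. Section 3 says "a standard of care FDA cleared adhesive sensor will be applied to each subject as a reference". Section 6.4.4 says "An FDA-cleared sensor will be placed on the" subject's foot, while Section 6.4.5 says "An FDA-cleared sensor may be placed on the" subject's foot.

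**The concern.** Applied literally to every available pair, the formula gives each infant a weight proportional to its number of valid pairs, which is roughly its recording length. A few infants recorded overnight could then carry much of a figure that appears to describe 25. If lab and home errors differ, the pooled value would describe neither setting. If they do not differ, the value would still be more variable, because one badly fitting sensor counts far more in a long recording than in a short one. With the unit and the grouping left open, both could be chosen after the data are seen. At stake would be the reading of the only numerical accuracy summary in the plan.

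**Working it through.** **The plan's own figures.** Section 7 states no A_RMS value, limit, variance or number of pairs. The target of 25 subjects cannot be re-derived, because the sponsor's error-distribution analysis is cited but not given. Only the comparison 25 > 15 can be checked, and it holds.

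**Inputs from the documents.** 25 subjects (Section 7); 1.5 h per lab recording (Section 6.4.4); at most 48 h at home (Section 6.3.3).

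**Assumptions, not in the documents.** k home-only infants, H home hours each (8 for one night, 16 for two), equal rates of valid pairs, and a reference sensor worn at home.

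**Weights.** Home share = kH / (kH + (25 - k) x 1.5). Kish effective number of infants = (sum of w)^2 / (sum of w^2), with w the recording hours.

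| k | H | Home share | Effective infants |
|---|---|---|---|
| 3 | 8 | 24/57 = 42% | 57^2/(3 x 64 + 22 x 2.25) = 13.5 |
| 3 | 16 | 48/81 = 59% | 81^2/(3 x 256 + 22 x 2.25) = 8.0 |
| 1 | 8 | 8/44 = 18% | 16.4 |
| 1 | 16 | 16/52 = 31% | 8.7 |
| 1 | 48 | 48/84 = 57% | 3.0 |
| 0, or no home reference | any | 0% | all lab recordings about equal |

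For k = 3, the variance of the pooled mean square is 25/13.45 = 1.9 or 25/8.03 = 3.1 times that of an equally weighted mean over all 25 infants. These ratios ignore sampling error within an infant, which longer recordings reduce, so they are upper-end values for the assumed design.

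**If the settings differ (assumed lab 2, home 3; k = 3).** Pooled A_RMS is sqrt(0.421 x 9 + 0.579 x 4) = 2.47 for one night and sqrt(0.593 x 9 + 0.407 x 4) = 2.64 for two.

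**If they do not differ (assumed one infant with RMS difference 4, the other 24 with 2; k = 3).**

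- Pooled, one night: sqrt(4 + 12 x 8/57) = 2.38 if that infant is at home, sqrt(4 + 12 x 1.5/57) = 2.08 if in the lab.
- Pooled, two nights: sqrt(4 + 12 x 16/81) = 2.52 or sqrt(4 + 12 x 1.5/81) = 2.05.
- Over random placement (3/25 = 12% at home), the expected mean square is 0.12 x 5.684 + 0.88 x 4.316 = 4.48 for one night and 0.12 x 6.370 + 0.88 x 4.222 = 4.48 for two. With equal weights it is (16 + 24 x 4)/25 = 4.48. Pooling therefore adds variability, not bias.

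**The alternative: split by setting, equal weight per infant.** In the same example, the home figure is sqrt((16 + 4 + 4)/3) = 2.83 if the poor-fit infant is at home and 2.00 if not. The lab figure is 2.00 or sqrt((16 + 21 x 4)/22) = 2.13.

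In a simulation with per-infant mean square b^2 + 2.25, b standard normal and no within-infant error (an assumed model), the SD of A_RMS was 0.08 for 22 lab infants and 0.21 for 3 home infants. For the pooled figure it was 0.10 with one night and 0.13 with two.

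**The case for a change.** The case for a change is that the sponsor thought accuracy worth a printed formula, that Section 7 cites an A_RMS error-distribution analysis as part of the reason for 25 subjects, and that this reasoning counts subjects, whereas pooling could leave 8 to 13.5 effective ones. Section 6.4.5 foresees continuous reference data at home, so home pairs are a real possibility. A few lines would close the gap at no cost in data, and the 8-hour nights used here are well below the 48-hour ceiling.

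Much of this stands. The index is undefined, the recording lengths do differ, and the arithmetic is right. Three things limit it.

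- **The link to 25 subjects shows relevance only.** The underlying calculation is not given, and the usability reason for 25 does not involve A_RMS.
- **The suggested estimator answers a different question.** It never produces the equally weighted 25-infant figure on which the 1.9 and 3.1 ratios rest, and it makes the home result more dependent on one infant. It also gives an infant with few surviving pairs the same influence as one with a full night, and it still needs a definition of a valid pair.
- **The reference-sensor wording is ambiguous, not contradictory.** If home recording is added to a lab session, as Section 6.3.3 allows, the lab reference already meets Section 3. The virtual screening in Section 6.4.3 makes home-only participation possible, so the ambiguity remains, but it concerns study conduct and not the formula.

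**Conclusion.** No change to the plan is needed. Section 7 leaves out a detail of notation and grouping for a descriptive statistic that may not be calculated at all. A_RMS has no acceptance limit or decision rule, and the form, fit and function objective in Section 5 does not use it.

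The effect ranges from zero (A_RMS not calculated, no paired home data, or settings not pooled) to 42% or 59% of pairs from 3 of 25 infants with one or two 8-hour nights. At the 48-hour ceiling a single home infant would supply 57%. The number of home infants, the hours recorded, the rate of valid pairs and the use of a home reference are all assumptions.

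An analyst who does calculate A_RMS would naturally say what i and n count and show lab and home results separately with per-infant values. Weighting infants equally or by recording length is a choice of what to estimate, with a precision cost either way, and no study conclusion turns on it.

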#### 7.1. Expected Dropout Rates

Subjects may not complete the study for various reasons, such as clinical screening test failure, at the investigator's or study staff's discretion, or because the subject does not want to continue the study. Due to the short duration and simple, noninvasive procedures of this study, there are limited expected dropouts.

However, the sample size may be increased to account for dropout rates during the study.

## 8. DATA MANAGEMENT

### 8.1. Data Management and Confidentiality

All documents associated with this protocol will be securely stored in a physical location or on password-protected computers. The confidentiality and retention of these documents will be protected to the extent provided and required by the law. All data will be de-identified before any statistical analysis. Only de-identified data will be shared with Masimo for research purposes stated in this protocol. Data collected by data capture software and data entered in case report form will be shared with Masimo via a secure, password-protected server that only study staff and Masimo study team members will have access to. Data will be retained for a minimum to 2 years following completion of the final analysis.

### 8.2. Source Documents

Source data is all information, original records of clinical findings, observations, or other activities in a clinical trial necessary for the reconstruction and evaluation of the trial. Source data are contained in source documents. Examples of these original documents and data records include: clinical and office charts, laboratory notes, memoranda, recorded data from automated instruments, and copies or transcriptions certified after verification as being accurate and complete.

